8 CONTENT OF REPORTS

8.1 PCD Final CSR

The following TLFs are produced for the PCD Final CSR (see Section 1.2):

- Section 6.2 Study Population: all TLFs
- Section 6.3 Efficacy: listing; tables of endpoints during the DBT Phase, i.e., those in Sections 6.3.1, 6.3.2, 6.3.3, 6.3.5.1, 6.3.5.2, and 6.3.5.3
- Section 6.3 Safety:
 - All listings
 - On-DBT, and post-DBT pre-OL rimegepant safety analysis periods: all tables and figures
 - On-OL rimegepant safety analysis period: tables of AE overview, AEs by worst intensity, AEs related to study drug by worst intensity, SAEs, AEs leading to study drug discontinuation, worst laboratory test abnormalities, and LFT elevations. No subgroup analyses.
 - Follow-up safety analysis period: tables of AE overview, AEs by worst intensity, and SAEs

- Section 6.4 Outcomes Research: table of MQoL total and domain scores at 24 hours postdose during the DBT Phase.

8.2 LSLV Final CSR

All TLFs specified in the SAP are produced for the LSLV CSR (see Section 1.2).

9 APPENDICES

9.1 Relevant Protocol Deviations

Relevant eligibility protocol deviations include the following categories:

- Previously treated with study drug in another BHV3000 (C495) multiple-dose study. Defined as subjects with (1) previous BHV3000 study subject identifiers from the Informed Consent/Demographic CRF, and (2) who took ≥ 1 dose of study drug (e.g., rimegepant or placebo) in a multiple-dose study.
- Randomized or treated with study drug under >1 subject identifier. These are identified from a Microsoft Excel file of protocol deviations extracted from the clinical trial management system (CTMS) by Sponsor Clinical Operations.
- No history of documented failure to ≥ 2 triptan medications or documented contraindication to the use of triptans (see Section 6.2.5.2)
- Migraine history issue, defined as any of the following subcategories:
 - ≤ 3 or ≥ 15 migraine days per month of any pain intensity in the 3 months prior to screening
 - ≥ 15 headache days per month in the 3 months prior to screening
 - ≥ 7 nonmigraine headache days per month in the 3 months prior to screening, if originally consented to Protocol Version 3 or higher. Defined as {number of headache days per month in the 3 months prior to screening} – {number of migraine days per month of any pain intensity in the 3 months prior to screening}.

These are based on the Migraine History CRF.

- Finding out of range during pretreatment, defined any as any of the following subcategories:
 - Females with a positive pregnancy test (see Section 6.4.2)
 - Estimated glomerular filtration rate (eGFR) according to the re-expressed abbreviated (4-variable) Modification of Diet in Renal Disease (MDRD) Study equation ≤ 40 mL/min/1.73m², if originally consented to Protocol Version 3 or lower *
 - eGFR according to the re-expressed abbreviated (4-variable) MDRD Study equation < 30 mL/min/1.73m², if originally consented to Protocol Version 4 or higher *
 - BMI ≥ 33 kg/m², if originally consented to Protocol Version 2 or lower *
 - BMI ≥ 35 kg/m², if originally consented to Protocol Version 3 or higher *

- C-SSRS suicidal ideation with active intent or plan to act, or suicidal behavior present. Defined as having a “yes” response to any of the following C-SSRS questions during pretreatment:
 - Suicidal ideation question 4 (active suicidal ideation with some intent to act, without specific) or 5 (active suicidal ideation with specific plan and intent)
 - Suicidal behavior question 1 (actual attempt), 3 (interrupted attempt), 4 (aborted attempt), 5 (preparatory acts or behavior), or 6 (suicidal behavior).

Responses to lifetime questions at the Screening Visit are excluded from analyses.

For the subcategories marked with “*”, all nonmissing values during the pretreatment analysis period must meet the deviation criteria in order to be considered a deviation.

Relevant subject management protocol deviations include the following categories:

- Randomization stratum discrepancies between the RTSM system and actual data, defined as any of the following subcategories:
 - RTSM value of “yes” and CRF value of “no” or missing
 - RTSM value of “no” and CRF value of “yes” or missing.

See Section 6.2.5.1 for history of clinically relevant CV disease status.

- Prophylactic migraine medication started or ended from 3 months before informed consent to randomization. Defined as either of the following:
 - informed consent date – 90 days ≤ imputed nonstudy medication start date ≤ RTSM randomization date
 - informed consent date – 90 days ≤ imputed nonstudy medication end date ≤ RTSM randomization date and nonstudy medication ongoing status is not “yes”.

See Section 6.2.6.3 for prophylactic migraine medications.

- DB study drug dosing noncompliance, defined as any of the following subcategories (see Section 6.2.6.2):
 - DB study drug taken but not randomized
 - DB study drug taken without having a qualifying migraine attack
 - DB study drug actually received different from randomized treatment assignment.
- OL rimegepant dosing noncompliance, defined as any of the following subcategories (see Section 6.2.6.2):
 - >1 OL rimegepant tablet taken on any 1 day
 - OL rimegepant taken without having a qualifying migraine attack
 - OL rimegepant taken but DB study drug never taken.
- Prohibited nonstudy medication taken on or after informed consent, defined as any of the following subcategories:

- Botulinum toxin type A
- Calcitonin gene-related peptide (CGRP) antagonist monoclonal antibody or small molecule #
- Ergotamine
- Lamotrigine
- Narcotic (barbiturate or opioid) #
- Paracetamol-containing product not taken as acute headache medication #. Defined as (1) preferred named name containing “paracetamol”, and (2) not categorized as nonstudy acute headache medication (see Section 6.2.6.3).
- Select moderate or strong cytochrome P450 3A4 (CYP3A4) inducer #
- Select strong CYP3A4 inhibitor #
- Triptan #.

Note that nonstudy medications with route of “topical” or “intraocular” are excluded.

- DBT rescue medication usage issue, defined as any of the following subcategories:
 - DBT rescue medication taken at or before 2 hours postdose #. Defined as first DBT rescue medication date/time – DB study drug date/time ≤ 2 hours, where both first DBT rescue medication date/time and DB study drug date/time must have nonmissing date and time. Note that the upper bound of the 2-hour postdose analysis window is not used.
 - Nonpermitted DBT rescue medication taken #. Identified from the latest version of C495 Permitted Acute Migraine Medication.xlsx or equivalent.
 - Paracetamol >2000 mg taken on any 1 day as DBT rescue medication. Paracetamol may be a single drug or a component in any combination drug.
- OLE rescue medication usage issue, defined as any of the following subcategories:
 - Nonpermitted OLE rescue medication taken #
 - Paracetamol >2000 mg taken on any 1 day as OLE rescue medication. Paracetamol may be a single drug or a component in any combination drug.

For the subcategories marked with “#”, preferred names are displayed alphabetically as additional subcategories. Refer to the Core SAP for additional details about prohibited nonstudy medication and permitted acute migraine (rescue) medication.

The RTSM randomization date is the reference date for “randomization”. If the RTSM randomization date is missing, then the study drug start date is used.

The protocol version to which subjects consented is determined from the Inclusion/Exclusion Criteria CRF.

9.2 Efficacy Day During the OLE Phase

For a given subject, each date during the OLE Phase analysis period is assessed whether it is an acute migraine medication day, acute migraine-specific medication day, or migraine day. Dates during the OLE Phase analysis period are defined by the interval [OLE Phase start date, OLE Phase end date] inclusive. See Section 7.1 for derived dates.

9.2.1 Medication Day During the OLE Phase

9.2.1.1 Acute Migraine Medication Day During the OLE Phase

Acute migraine (rescue or non-rescue) medication days are identified from nonstudy medication CRF data and eDiary data.

Nonstudy acute headache medications taken during the OLE Phase and eDiary measurement dates during the OLE Phase are selected (see Sections 6.2.6.3 and 7.1).

Let X denote a date in the OLE Phase interval defined in Section 9.2. Then X is classified as an acute migraine medication day during the OLE Phase if any of the following criteria is met:

- X is an acute migraine-specific medication day (see Section 9.2.1.2)
- X is a migraine day (see Section 9.2.2) on which any of the following also occur:
 - Imputed medication start date $\leq X \leq$ imputed medication end date, if any given select nonstudy acute headache medication has medication frequency of QD, BID, TID, QID, QAM, or QHS
 - X is equal to the imputed start date or imputed end date, if any given select nonstudy acute headache medication does not have medication frequency of QD, BID, TID, QID, QAM, or QHS
 - X is an eDiary measurement date with “yes” response to the question about other medication taken to treat headache or aura from the eDiary Migraine question category (see Section 7.4).

All select nonstudy medication records and eDiary measurement dates are compared to X to determine whether X is an acute migraine medication day.

Acute migraine medication days are a subset of migraine days (see Section 9.2.2).

9.2.1.2 Acute Migraine-Specific Medication Day During the OLE Phase

Acute migraine-specific medication days are identified from nonstudy medication CRF data and eDiary data.

Nonstudy acute migraine-specific medications taken during the OLE Phase and OL rimegepant dates are selected (see Sections 6.2.6.3 and 7.1).

Let X denote a date in the OLE Phase interval defined in Section 9.2. Then X is classified as an acute migraine-specific medication day during the OLE Phase if any of the following criteria is met:

- Imputed medication start date $\leq X \leq$ imputed medication end date, if any given select medication has medication frequency of QD, BID, TID, QID, QAM, or QHS
- X is equal to the imputed start date or imputed end date, if any given select medication does not have medication frequency of QD, BID, TID, QID, QAM, or QHS
- X is an OL rimegepant date.

All select nonstudy medication records and OL rimegepant dates are compared to X to determine whether X is an acute migraine-specific medication day.

Acute migraine-specific medication days are a subset of acute migraine medication days and migraine days (see Sections 9.2.1.1 and 9.2.2).

9.2.2 Migraine Day During the OLE Phase

Let X denote a date in the interval defined in Section 9.2. Then X is classified as a migraine day during the OLE Phase if either of the following criteria is met:

- X is an eDiary measurement date with migraine headache pain intensity of mild, moderate, or severe from the eDiary Migraine question category (see Section 7.4.2)
- X is an acute migraine-specific medication day (see Section 9.2.1.2).

If there are multiple headache pain intensities from the Migraine or Headache (Non-migraine) question category on the same eDiary measurement date that is a migraine day, then the worst (greatest) headache pain intensity is selected based on the hierarchy of severe, moderate, or mild.

9.3 Analyses of Reliability of Rimegepant Effect in the OLE Phase

9.3.1 EQMAs

A qualifying migraine attack is defined as an attack of moderate or severe migraine headache pain intensity that is first treated with study drug. Each qualifying migraine attack is derived from a distinct set of Migraine question category parameters at the time of study drug dosing that has both of the following parameter values in the same set:

- 1) Migraine headache pain intensity of moderate or severe
- 2) Other medication taken to treat headache or aura status of “no”.

The set of Migraine question category parameters at the time of study drug dosing is linked to an eDiary reported study medication date/time (see Sections 7.4 and 7.4.1.1).

An EQMA is defined as a qualifying migraine attack in the appropriate phase analysis period (DBT or OLE) with a nonmissing MQoL Question 16 value at 24 hours postdose in the appropriate outcomes research analysis period (DBT or OLE). The eDiary measurement date/time for a given qualifying migraine attack is the eDiary reported study medication

date/time to which it is linked, and is used to determine whether there is a nonmissing MQoL Question 16 value in the corresponding 24-hour analysis window (see Section 7.4.4) in the outcomes research analysis period. If a subject has >1 MQoL set in the same analysis window, then the MQoL set with the earliest eDiary finding date/time and nonmissing MQoL Question 16 value in the outcomes research analysis period is selected for that qualifying migraine attack.

During the OLE Phase, the first 5 EQMAs $\geq X$ hours apart in the OLE Phase are identified as follows:

- 1) All EQMAs during the OLE Phase are sorted by the (1) eDiary measurement date (ignoring time), and (2) eDiary finding date/time.
- 2) If a subject has >1 EQMA on the same eDiary measurement date, then the EQMA with the earliest eDiary finding date/time is selected.
- 3) The first 5 EQMAs $\geq X$ hours apart in the OLE Phase are selected based on the first 5 eDiary measurement date/times being $\geq X$ hours apart.
 - $X = 23$ in the main analysis, whereas $X = 47$ in the sensitivity analysis (see Section 6.5.1.1). The cutoffs of 23 and 47 hours align with the lower bounds of the 24-hour and 48-hour postdose analysis windows, respectively (see Table 7).
 - The first EQMA is included in both analyses, and is the starting point.
 - The next EQMA $\geq X$ hours apart from the first EQMA is included in the analysis, and becomes the new starting point.
 - The iterative process continues until the first 5 EQMAs $\geq X$ hours apart are selected. See example below.

Example:

EQMA	eDiary Measurement Date/Time	Include in Main Analysis	Include in Sensitivity Analysis
1	01JAN2024:10:25	Yes	Yes
2	02JAN2024:08:32	No	No
3	03JAN2024:08:35	Yes	No
4	04JAN2024:06:22	No	Yes
5	05JAN2024:11:26	Yes	No

9.3.2 SAS Code: Linear Mixed Effects Model With Repeated Measures

Consider the following variables used to evaluate the MQoL overall change using a linear mixed effects model with repeated measures:

- mqol: MQoL Question 16 value; continuous variable (integer)
- irndstr: imputed randomization stratum; categorical variable with levels of 1 and 2 to denote yes and no, respectively (see Section 6.2.5.1)
- eqma: EQMA; categorical variable with levels of 1 to 5

- resiol: OLE rescue medication or intervening OL rimegepant taken at or before the MQoL Question 16 value; categorical variable with levels of 1 and 2 to denote yes and no, respectively
- usubjid: unique subject identifier; categorical variable.

Then the SAS code is as follows:

```
proc mixed empirical;  
class usubjid irndstr eqma resiol;  
model mqol = irndstr resiol eqma eqma*resiol;  
repeated eqma / subject=usubjid type=un; /* unstructured */  
lsmeans eqma*resiol / alpha=0.05 cl;  
run;
```

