 - **A qualifying migraine attack in the OLE Phase is defined as a migraine attack of moderate or severe headache pain intensity that is first treated with open-label study drug, i.e., acute migraine medication is not taken before taking open-label study drug.**
 - In association with each of the ***First 5 Qualifying Migraine Attacks***, subjects are required to use the eDiary to complete the MQoL Questionnaire at 24 hours after dosing with open-label study drug. In the event an MQoL Questionnaire is not completed for any of the first 5 qualifying migraine attacks (eg, inadvertently missed), MQoL Questionnaires will be collected for subsequent qualifying migraine attacks until a total of 5 MQoL Questionnaires are completed.
 - If migraine-associated symptoms persist beyond 2 hours after dosing with open-label study drug, subjects may use permitted acute migraine medication (see [Section 16.3, Appendix 3](#)) for the purposes of rescue, as needed and in accordance with the standard of care. *All dosing of rescue medication (permitted or exclusionary), as defined in [Section 6.4.4](#), is to be recorded on the Rescue Medication paper diary.*

In the DBT Phase, the study drug will be blinded 75 mg ODT of rimegepant or matching placebo. The study will randomize approximately 600 subjects in a 1:1 ratio to blinded rimegepant or matching placebo in the DBT Phase. Randomization will be stratified by history of clinically relevant CV disease (yes or no; see [Section 7.1.6](#)). In addition, randomization of subjects in the CV subgroup (“yes” category) will be capped at 15%. In the OLE Phase, the study drug will be 75 mg ODT of open-label rimegepant.

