7.1.6. Method of Assigning Subject Identification

The Investigator or designee will need to access the Randomization and Trial Supply Management (RTSM system) in order to register each subject. Initially, after informed consent is obtained at the Screening Visit, the Investigator or designee will enter the subject into the study and obtain a subject number assignment.

At the Baseline Visit, eligible subjects will be randomized in a 1:1 ratio to rimegepant or placebo. Randomization will be stratified by history of clinically relevant CV disease (yes or no). In addition, randomization of subjects in the CV subgroup (“yes” category) will be capped at 15%. Subjects are to be categorized as “yes” if they meet the criteria for being in the CV subgroup (see [Section 16.4, Appendix 4](#), Contraindication: Cardiovascular Events, Conditions, and Procedures). Otherwise, subjects are to be categorized as “no”.

Once a subject completes the study, or if a subject is discontinued early from the study, the Investigator or designee must access the RTSM to document discontinuation of the subject from participation in the study.

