 - Subjects are categorized as “yes” if they have history of CV event, condition, or procedure (i.e., are in category 1, 2, or 3 in Section 6.2.5.2 “History of CV Events, Conditions, Procedures, and Other Risk Factors”).
 - Otherwise, subjects are categorized as missing if they have “no” or missing response to the question “Was a Cardiovascular History assessed?” on the History of CV Events, Conditions, Procedures, and Other Risk Factors CRF.
 - Otherwise, subjects are categorized as “no”.
- Imputed randomization stratum #: history of clinically relevant CV disease (yes, no). This is an efficacy and safety subgroup of interest (see Sections 4.3.1 and 4.3.2).
 - If the randomization stratum value based on actual data is missing, then it is imputed with the randomization stratum value from the RTSM system. Otherwise, the imputed randomization stratum value is equal to the randomization stratum value based on actual data.
 - A footnote specifies that “# Missing randomization stratum based on actual data is imputed with the randomization stratum from the RTSM system. Used in subgroup

analyses and efficacy/outcomes research analyses that use randomization stratum as a variable in models or risk stratification.”.

- History of documented failure to ≥ 2 triptans with ≥ 1 reason due to lack of efficacy. This is an efficacy subgroup of interest (see Section 4.3.1).
 - Subjects are categorized as “yes” if they meet the applicable criteria defined in Section 6.2.5.2 “Triptan-Unsuitable Criteria”, i.e., they are in the “History of documented failure to ≥ 2 triptans” category and “lack of efficacy” subcategory.
 - Otherwise, subjects are categorized as missing if they have “no” or missing response to the question “Was a Cardiovascular History assessed?” on the History of CV Events, Conditions, Procedures, and Other Risk Factors CRF.
 - Otherwise, subjects are categorized as “no”.

Note that race and ethnicity are summarized only for subjects in the United States of America, and percentages are calculated against the number of subjects in the United States of America.

The frequency cross table of randomization stratum (history of clinically relevant CV disease) from the RTSM system versus actual data is provided for the full analysis set by as-randomized treatment group and overall. Categories are:

- RTSM value of “yes” and CRF value of “yes”
- RTSM value of “yes” and CRF value of “no” or missing
- RTSM value of “no” and CRF value of “no”

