6.5.1.2 MQoL Scores by EQMA During the DBT and OLE Phases

The table of MQoL total, domain, and overall change (Question 16) scores at 24 hours postdose by EQMA is provided for the DBT efficacy analysis set by treatment group/OL rimegepant and

overall after (1) the single EQMA in the DBT Phase, and (2) each of the first 5 EQMAs ≥ 23 hours apart in the OLE Phase. Results support exploratory objectives #1 and #2.

For the single EQMA in the DBT Phase, analyses are based on the DBT efficacy analysis set with MQoL eDiary measurement dates in the DBT Phase analysis period.

For the first 5 EQMAs ≥ 23 hours apart in the OLE Phase, analyses are based on OLE efficacy analysis set with MQoL eDiary measurement dates in the OLE outcomes research analysis period.

Refer to the Core SAP for the calculation of the MQoL total and domain scores, and TLF contents.

6.5.1.3 *MQoL Overall Change in Migraine Symptoms During the OLE Phase Using Model Estimation*

Analyses are based on the first 5 EQMAs ≥ 23 hours apart in the OLE Phase for the OLE efficacy analysis set with ≥ 1 MQoL in the OLE outcomes research analysis period.

A linear mixed effects model with repeated measures and the following attributes is used:

- Variables: MQoL Question 16 value as the dependent variable; imputed randomization stratum, categorical EQMA (i.e., 1 to 5 of the OLE Phase), rescue medication or intervening OL rimegepant use at or before the MQoL Question 16 value (yes, no), and migraine attack-by-rescue medication/intervening OL rimegepant use as fixed effects. If there are sparse data within a randomization stratum, then this variable may be excluded.
- Covariance structure for repeated measures accounting for within-subject correlated errors: unstructured. If the model fails to converge or cannot be fit with an unstructured covariance structure, then a first-order autoregressive with homogeneous variances ("AR(1)") structure is used.
- Standard error (SE) estimation method: Huber-White "sandwich" (refer to the Core SAP).

The table displays the following model estimates by EQMA: least-squares mean (LSM), SE, and 95% CI. See Section 9.3.2 for the SAS code.

A line plot with error bars displays the LSM MQoL overall change in migraine symptoms on the y-axis versus EQMA during the OLE Phase on the x-axis by rescue medication/intervening OL rimegepant use at or before the MQoL Question 16 value (yes, no). Error bars denote 95% CIs for LSMs.

6.5.2 *MSQ*

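### The open-label mixed model averages cardiovascular history yes and no 50:50, although the yes stratum is capped at 15%, so its displayed means and intervals do not match the enrolled mix

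*SAP*

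**What the plan says.** SAP 6.5.1.3 describes a repeated-measures linear mixed model for the Question 16 score over the first 5 evaluable qualifying attacks (EQMAs). SAP 9.3.2 prints the code.

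- CV history is a class variable: "class usubjid irndstr eqma resiol", with "irndstr: imputed randomization stratum; categorical variable with levels of 1 and 2 to denote yes and no, respectively".
- It enters additively, with no interaction: "model mqol = irndstr resiol eqma eqma*resiol".
- Means are requested with "lsmeans eqma*resiol / alpha=0.05 cl".
- SAP 6.5.1.3 reports them: "The table displays the following model estimates by EQMA: least-squares mean (LSM), SE, and 95% CI". A line plot shows the same means by rescue or intervening-dose use, with the 95% intervals as error bars.

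Protocol 7.1.6 sets the size of the stratum: "In addition, randomization of subjects in the CV subgroup (“yes” category) will be capped at 15" per cent. The value analysed comes from the CRF. SAP 6.2.5.1 states the exception: "If the randomization stratum value based on actual data is missing, then it is imputed with the randomization stratum value from the RTSM system".

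SAP 6.5.1.3 also lets the stratum be left out of the model if its data are sparse, but sets no threshold. Neither section mentions how the strata are to be weighted in the means.

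**The concern.** With no weighting option, PROC MIXED averages the levels of every other class effect equally. CV history yes then has weight 0.50 in each mean against at most about 0.15 among randomized subjects, which is 0.50/0.15 = 3.3 times its share.

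The plan's neighbouring analyses do not do this. The Mantel-Haenszel comparisons in SAP 6.3 weight strata according to their size. The response rates in SAP 6.5.1.1 are crude proportions of evaluable subjects, so they carry the observed CV mix. The model means concern the same question and the same attacks as those rates, but refer to a different population, and the SAP does not say so.

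The sparse-data clause adds to this. If the stratum is kept, the means refer to a 50:50 population; if it is dropped, they refer to the observed mix. A choice with no stated threshold thus changes what is estimated. At stake are the level of the displayed means and the width of their intervals.

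**Working it through.** The documents give no numerical figure for this model, so there is none to reproduce.

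**Inputs from the documents.** Model terms and LSMEANS statement (SAP 9.3.2); 15% cap (Protocol 4.1 and 7.1.6); about 510 subjects expected in the extension (SAP 2.1); 5 attacks per subject.

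**Assumed inputs.** 480 analysed subjects, Question 16 SD 1.4, exchangeable within-subject correlation 0.4, rescue or an intervening dose in 25% of attacks, and a CV share *q* of 15% or 10%. The SD cancels in the ratios. Standard errors are model-based generalized least squares; the SAP specifies sandwich errors and an unstructured covariance, so the ratios are approximations.

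**Step 1: level.** Let *b* be the mean Question 16 score in CV yes minus CV no.

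- Equal margins: cell mean = (CV-no cell mean) + 0.5*b*
- Observed margins: cell mean = (CV-no cell mean) + *q b*
- Shift = (0.5 − *q*) × *b*

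At *q* = 0.15 the multiplier is 0.35. For assumed differences of 0.25, 0.5 and 1.0 points, the shift is 0.09, 0.18 and 0.35 points. If *b* = 0 it is zero. Because CV history has no interaction in the model, all 10 means move by the same amount. A simulated data set with 76 of 510 subjects CV yes confirmed this: the estimated *b* was 0.2015 and every mean moved by (0.5 − 76/510) × 0.2015 = 0.0707.

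**Step 2: precision.** To a close approximation, the observed-margin mean is uncorrelated with the estimate of *b*, so

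SE(equal)² ≈ SE(observed)² + (0.5 − *q*)² × SE(*b*)²

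SE(*b*) = 1.4 × √[(1 + 4 × 0.4)/5] × √(1/n_yes + 1/n_no).

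- *q* = 15% (72 and 408 subjects): 1.4 × 0.7211 × 0.1278 = 0.129
- *q* = 10% (48 and 432 subjects): 1.4 × 0.7211 × 0.1521 = 0.154

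The observed-margin SE is 0.0711 in no-rescue cells and 0.1133 in rescue cells.

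| CV share | Cell | SE, observed margins | SE, equal margins | Ratio |
|---|---|---|---|---|
| 15% | no rescue | 0.0711 | √(0.00506 + 0.00204) = 0.0842 | 1.185 |
| 15% | rescue | 0.1133 | √(0.01284 + 0.00204) = 0.1220 | 1.077 |
| 10% | no rescue | 0.0711 | √(0.00506 + 0.00378) = 0.0939 | 1.32 |
| 10% | rescue | 0.1133 | √(0.01284 + 0.00378) = 0.1289 | 1.14 |

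The 95% half-width at the cap is 1.96 × 0.0842 = 0.165 against 1.96 × 0.0711 = 0.139 without rescue, and 0.239 against 0.222 with rescue.

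**Step 3: sensitivity.** With 510 subjects, correlation 0.2 to 0.5 and rescue in 15% to 30% of attacks, the ratio at a 15% share is 1.13 to 1.24 without rescue and 1.02 to 1.12 with rescue. At a 10% share it is 1.21 to 1.40 and 1.04 to 1.20.

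**Step 4: differences.** In the difference between two of the ten means, the CV term cancels whatever its weight. Both the estimate and its standard error are unchanged.

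**The case against.** The strongest reply is that equal margins are a legitimate target and the SAP fixes them by printing the code. The intervals are then correct for that target, and the SAP leaves no post hoc choice of weights. This stands in part: nothing is miscalculated. But the text never says that a half-CV population is intended, and nothing else in the plan uses one.

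A second reply is that little depends on this model, and that also stands. A reader might infer that the weighting distorts how the effect holds up over the five attacks. It does not, because all means move together. A reader might also take the model to support other secondary objective 1. The SAP attaches that objective to the response-rate table in 6.5.1.1; section 6.5.1.3 makes no such claim, and the reliability criterion uses percentages only.

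Third, a reader might take the by-EQMA wording in 6.5.1.3 to require one row per attack, pooled over rescue use, and object that a default mean would weight rescue 50:50 as well. If rescued attacks scored 1.5 points lower, that would move the mean by (0.50 − 0.25) × 1.5 = 0.375 points. But the SAP contains no such statement, and rows by attack and rescue use satisfy the wording and match the plot.

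Fourth, a CV share of 5% would give larger ratios. That is roughly 25 of 510 subjects, where the sparse-data clause could plausibly remove the stratum, so that case is no basis for sizing the problem.

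**Conclusion.** The point holds as a minor one on a descriptive, supportive analysis. As coded, each mean and interval refers to a population that is half CV-history, against a cap of 15%. At the cap, standard errors are about 19% larger in no-rescue cells and 8% larger in rescue cells, which adds about 0.03 and 0.02 points to the half-width on a seven-category item. At a 10% share the increases are about 32% and 14%. These figures rest on the assumed correlation and rescue rate. The loss of precision needs no CV effect; the shift in level does, and the documents do not support saying that the means are in fact shifted.

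Two limits remain. The cap applies to the stratum recorded at randomization while the model uses CRF data, so the analysed share may differ somewhat from 15%, though nothing suggests it approaches 50%. The Core SAP was not available; the printed code carries no weighting option. No hypothesis test, comparison between attacks, rescue contrast or reliability conclusion changes.

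**What to change.** In SAP 9.3.2, change the statement to `lsmeans eqma*resiol / om alpha=0.05 cl;`. In SAP 6.5.1.3, add a sentence saying that the means use observed margins for the CV stratum. If a row per attack pooled over rescue use is wanted, request it explicitly, also with observed margins. If equal weighting is intended, say so and give the reason.

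The cost is one SAS option and one sentence. No data collection, sample size or test changes. Observed margins also make the means depend much less on whether the sparse-data clause is used.
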